9. PROTECTION OF HUMAN SUBJECTS

All study materials, including the research protocol and paper-version of the eCRF, will be reviewed by a central IRB prior to any data abstraction including field-testing of the eCRF. Providers are required to be able to participate in research monitored by a central IRB. At all times, patients' PHI will be kept confidential in accordance with HIPAA. The eCRF will not capture any data related to the patients' name, full date of birth, social security number, health insurance plan number, medical record number, or other such PHI although PHI related to dates of treatment or clinical events will be collected. A waiver for obtaining informed consent from the provider or patient is sought for this research given the minimal risk imposed by the data elements to be collected.

This study was designed and shall be implemented and reported in accordance with the Guidelines for Good Pharmacoepidemiology Practices of the International Society for Pharmacoepidemiology (ISPE) 2008, the STROBE (Strengthening the Reporting of Observational Studies in Epidemiology) guidelines,¹² and with the ethical principles laid down in the Declaration of Helsinki.

9.1. Patient Information

All parties will comply with all applicable laws, including laws regarding the implementation of organizational and technical measures to ensure protection of patient personal data. Such measures will include omitting patient names or other directly identifiable data in any reports, publications, or other disclosures, except where required by applicable laws.

The personal data will be stored at the study site in encrypted form and will be password protected to ensure that only authorized study staff have access. Cardinal Health will implement appropriate technical and organizational measures to ensure that the personal data can be recovered in the event of disaster. In the event of a potential personal data breach, the study site shall be responsible for determining whether a personal data breach has in fact occurred and, if so, providing breach notifications as required by law.

To protect the rights and freedoms of natural persons with regard to the processing of personal data when study data are compiled for transfer to Pfizer and other authorized parties, patient names will be removed and will be replaced by a single, specific, numerical code based on a numbering system defined by Pfizer. All other identifiable data transferred to Pfizer or other authorized parties will be identified by this single patient-specific code. The investigator site will maintain a confidential list of patients who participated in the study, linking each patient's numerical code to his or her actual identity. In case of data transfer, Pfizer will maintain high standards of confidentiality and protection of patients' personal data consistent with the Clinical Study Agreement and applicable privacy laws.

9.2. Patient Consent

As this study involves anonymized structured or unstructured data, which according to applicable legal requirements do not contain data subject to privacy laws, obtaining informed consent from patients by Pfizer is not required.

9.3. Patient Withdrawal

Not applicable.

9.4. Institutional Review Board (IRB)/Independent Ethics Committee (IEC)

The study will be submitted to a centralized independent IRB in the U.S. for approval of the methodological approach and for obtaining a waiver of informed consent. An exemption will be sought on the basis that the study will collect only secondary data, no PHI will be collected and all data will be de-identified.

9.5. Ethical Conduct of the Study

The study will be conducted in accordance with legal and regulatory requirements, as well as with scientific purpose, value and rigor and follow generally accepted research practices described in Guidelines for Good Pharmacoepidemiology Practices (GPP) issued by the ISPE, Good Practices for Outcomes Research issued by the International Society for Pharmacoeconomics and Outcomes Research (ISPOR), the STROBE (Strengthening the Reporting of Observational Studies in Epidemiology) guidelines, and with the ethical principles laid down in the Declaration of Helsinki.

10. MANAGEMENT AND REPORTING OF ADVANCE EVENTS/ADVANCE REACTIONS

This study protocol requires human review of patient-level unstructured data; unstructured data refer to verbatim medical data, including text-based descriptions and visual depictions of medical information, such as medical records, images of physician notes, neurological scans, X-rays, or narrative fields in a database. The reviewer is obligated to report adverse events (AEs) with explicit attribution to any Pfizer drug that appear in the reviewed information (defined per the patient population and study period specified in the protocol). Explicit attribution is not inferred by a temporal relationship between drug administration and an AE, but must be based on a definite statement of causality by a healthcare provider linking drug administration to the AE.

The requirements for reporting safety events on the non-interventional study (NIS) adverse event monitoring (AEM) Report Form to Pfizer Safety are as follows:

- All serious and non-serious AEs with explicit attribution to **any Pfizer drug** that appear in the reviewed information must be recorded on the CRF and reported, within 24 hours of awareness, to Pfizer Safety using the NIS AEM Report Form.
- Scenarios involving drug exposure, including exposure during pregnancy, exposure during breast feeding, medication error, overdose, misuse, extravasation, lack of efficacy, and occupational exposure associated with the use of a Pfizer product must be reported, within 24 hours of awareness, to Pfizer Safety using the NIS AEM Report Form.

For these AEs with an explicit attribution or scenarios involving exposure to a Pfizer product, the safety information identified in the unstructured data reviewed is captured in the Event Narrative section of the report form, and constitutes all clinical information known regarding these AEs. No follow-up on related AEs will be conducted.

All the demographic fields on the NIS AEM Report Form may not necessarily be completed, as the form designates, since not all elements will be available due to privacy concerns with the use of secondary data sources. While not all demographic fields will be completed, at the very least, at least one patient identifier (eg, gender, age as captured in the narrative field of the form) will be reported on the NIS AEM Report Form, thus allowing the report to be considered a valid one in accordance with pharmacovigilance legislation. All identifiers will be limited to generalities, such as the statement “A 35-year-old female...” or “An elderly male...” Other identifiers will have been removed.

Additionally, the onset/start dates and stop dates for “Illness”, “Study Drug”, and “Drug Name” may be documented in month/year (mmm/yyyy) format rather than identifying the actual date of occurrence within the month /year of occurrence in the day/month/year (DD/MMM/YYYY) format.

All research staff members must complete the following Pfizer training requirements:

- “*YRR Training for Vendors Working on Pfizer Studies (excluding interventional clinical studies and non-interventional primary data collection studies with sites/investigators)*”.

These trainings must be completed by research staff members prior to the start of data collection. All trainings include a “Confirmation of Training Certificate” (for signature by the trainee) as a record of completion of the training, which must be kept in a retrievable format. Copies of all signed training certificates must be provided to Pfizer.

Re-training must be completed on an annual basis using the most current Your Reporting Responsibilities training materials.

11. PLANS FOR DISSEMINATING AND COMMUNICATING STUDY RESULTS

In the event of any prohibition or restriction imposed (eg, clinical hold) by an applicable competent authority in any area of the world, or if the investigator is aware of any new information which might influence the evaluation of the benefits and risks of a Pfizer product, Pfizer should be informed immediately.

13. LIST OF TABLES

None.

14. LIST OF FIGURES

None.

15. ANNEX 1. LIST OF STAND ALONE DOCUMENTS

None.

16. ANNEX 2. ADDITIONAL INFORMATION

Not applicable.

1 INTRODUCTION

Since the initial approval of palbociclib in February 2015 for the treatment of hormone receptor (HR)-positive, human epidermal growth factor receptor 2 (HER2)-negative advanced or metastatic breast cancer (MBC) in combination with an aromatase inhibitor (AI) as initial endocrine based therapy in postmenopausal women or in combination with fulvestrant, real-world observational studies have robustly described treatment patterns, dose modifications, and tolerability across multiple distinct retrospective databases.¹⁻⁴ Estimates of the clinical benefit (disease response, progression-free survival [PFS]) of palbociclib plus letrozole (palbociclib +LET) have been limited, however as these dataset cover the first two-years post approval which falls short of the 24.8 months PFS of palbociclib+LET observed in PALOMA-2.⁵ A recently published retrospective chart review study found the real-world estimate of the 24-month progression-free rate of 64.3%.⁴ With now more than 3 years of follow-up for the first palbociclib-treated patient, additional long term clinical benefit evidence can be generated leading to more precise estimates of PFS are available.

Another limitation of the previously conducted real-world research is the lack of a comparator arm for contextualizing the effects of palbociclib+LET therapy. Aromatase inhibitor (AI) monotherapies continue to be prescribed for a large number of HR-positive/HER2-negative MBC patients in lieu of the results of the PALOMA trials.⁶ The differences in the demographic and clinical disease characteristics of women receiving first-line (1L) treatment with LET versus those prescribed palbociclib+LET have not been explored.

Finally, since the completion of the previously described real-world research, ribociclib was approved in same indication as ribociclib (March 2017).⁷ No real-world data on clinical characteristics, treatment patterns (including dose reductions and rates of discontinuation), or early estimates of rates of progression have been explored in a real-world cohort of ribociclib+AI treated patients.

2 STUDY DESIGN

Patient demographics, clinical characteristics, treatment patterns pre- and post-palbociclib, laboratory monitoring, dosing patterns (and rationale for dosing changes), and clinical outcomes, including disease response and PFS will be described for locoregional recurrent or metastatic patients receiving palbociclib+LET as 1L, [REDACTED]

[REDACTED] The data will be collected through a physician-led, retrospective chart review. Providers will identify patients meeting the study selection criteria and abstract data from his/her patients' medical records into an electronic case report form (eCRF). Cardinal Health will conduct data verification via telephone and electronic follow-up. [REDACTED]

CCI

[REDACTED]

- 1) Presence of visceral metastases at the initiation of initial endocrine therapy for MBC
- 2) Receipt of prior neo/adjuvant endocrine therapy
- 3) De novo metastatic disease, ≤ 12 months disease free interval since prior neo/adjuvant treatment, >12 months disease free interval since prior neo/adjuvant treatment

CCI

[REDACTED]

2.1 STUDY POPULATION

CCI

[REDACTED]

- 1) Patients treated with palbociclib+LET as initial endocrine therapy for MBC per the palbociclib U.S. FDA approval label;

CCI

[REDACTED]

The target sample size for each of the three cohorts is 200 patients. Table 1 illustrates the selection criteria for each of the cohorts. Patients must meet all of the following inclusion criteria to be eligible for inclusion in the study. No exclusion criteria will be imposed for the selection of patients.

Table 1. Cohort Selection Criteria.

Palbociclib+LET	CCI
Diagnosed with locoregional recurrent or metastatic female breast cancer	
Pathologically confirmed HR-positive/HER2-negative tumor	
Received treatment with palbociclib in combination with LET as initial endocrine-based therapy for advanced/metastatic breast cancer 
 - Initiated treatment with palbociclib at least 3 months following the provider's first use of palbociclib after 03 Feb 2015 - At least 1 month of follow-up data after initiation of palbociclib 	
Postmenopausal (or receiving surgical or medical treatment to induce menopause) at the time of initiation of 1L treatment for locoregional recurrent or BMC	
≥18 year old at initiation of endocrine therapy	

Patient eligibility will be confirmed by the treating physician. Providers may complete a maximum of 20 eCRFs. Providers will be asked to randomly select patients from the pool of eligible patients and verify that they have performed random patient selection.

2.2 DATA SOURCE

Providers will complete data abstraction into the eCRF using all structured and unstructured data, including laboratory, pathology, and radiology files from the selected

patients' electronic health records. The eCRF is designed to allow providers to efficiently move through the patient chart or electronic medical record (EMR) based on the journey of the patient through the course of their disease. All study data are secondary data that will have been collected retrospectively from existing clinical data originally collected as part of routine care. Unknown or missing options will be provided as applicable or when a data element is not required for the patient to be eligible.

All submitted eCRFs will be subject to at least one data quality control assessment. First, all submitted data will be analysed to identify response patterns which substantially deviate from the population average. A list of those variables which will be examined through this manner of assessment is presented in Section 5.1. Next, a random sample of 10% of the submitted eCRFs will be reviewed by clinical research team members to identify any missing data, questionable data such as implausible dates, or values for variables which are inconsistent with known clinical parameters. Records with flagged data will be presented to the providers for review and update. Finally, 10% of submitted eCRFs will have providers re-enter data for three selected variables (see Section 5.1). Records which cannot be verified will be removed from the analytical dataset. Should >50% of the eCRFs submitted by a provider be flagged for review and the provider is unable to validate all of the records all eCRFs from that provider will be removed from the dataset. Replacement sampling will not be conducted.

The eCRF conforms to the rules and regulations of the Health Insurance Portability and Accountability Act (HIPAA) of 1996 governing the abstraction and storage of protected health information (PHI). No PHI will be collected in the course of the chart review or stored in the eCRF.

2.3 TREATMENT/COHORT LABELS

In this study, a line of therapy is defined as one or more anti-cancer agents given in combination over a period of time. Providers will be informed as to the definition of a regimen *but will make the determination themselves as to what constituted a line of therapy for the treatment of locoregional recurrent or metastatic breast cancer.* The first line of therapy is the first regimen initiated following the diagnosis of locoregional recurrent or metastatic breast cancer. Neoadjuvant or adjuvant regimens will not be considered a line of therapy in locoregional recurrent or metastatic setting.

2.4 STUDY OBJECTIVES

Primary Objectives

Among MBC patients receiving palbociclib+LET according to its labeled indication as initial endocrine therapy for MBC, the research objectives are to:

- 1) Describe the demographic and clinical characteristics of patients
 - a. Demographic characteristics will include age, race/ethnicity, body mass index, insurance status, state of residence at the date of MBC diagnosis, and palbociclib initiation. Employment status will be assessed to the extent documented in the

record. Overall duration of follow-up (months) from the initiation of palbociclib+LET will be presented.

b. Clinical characteristics will include year of breast cancer and MBC diagnosis, AJCC stage at initial diagnosis, sites of metastatic disease at MBC diagnosis and palbociclib+LET initiation (including nodal status), menopausal status at MBC diagnosis and initiation of palbociclib+LET, verification of HER2 and ER/PR status, ECOG performance status, comorbidities (based on Charlson comorbidity index listing) at initiation of palbociclib+LET, and treatments received in the neoadjuvant or adjuvant setting (chemotherapy, hormone therapy, surgery, radiation therapy).

2) Describe the frequency of laboratory monitoring during treatment

- a. Note that complete blood count (CBC) monitoring and cardiac function monitoring will be assessed, but lab results/values will not be assessed under this objective.
- b. Evaluate the extent of laboratory monitoring using CBC during the first three cycles of 1L treatment
- c. Assess the frequency of cardiac toxicity monitoring using electrocardiogram, liver function panels, and electrolytes during the first three cycles of 1L treatment
 - i. The frequency of assessment of cardiac monitoring by each method will be evaluated during the initial endocrine-based therapy for MBC

3) Describe treatment patterns in terms of palbociclib+LET dosing, cycles received, and post-discontinuation treatment regimens

- a. Palbociclib dosing will include description of the starting dose, dose adjustment (increase and decrease, interruptions), time to dose adjustment for palbociclib, and rationale for dose adjustment (provider interpretation)
- b. Duration of palbociclib in terms of the number of cycles completed prior to the discontinuation of initial treatment for MBC
- c. Primary rationale for the discontinuation of palbociclib+LET per provider interpretation
- d. Treatment patterns includes the distribution of regimens administered, by line, from MBC diagnosis through the end of the medical record
- e. Treatment patterns also includes the sequence of treatments across lines, from MBC diagnosis through the end of the medical record

4) Describe the rate of objective disease response during initial endocrine-based therapy

- a. Tumor response will be classified per provider report for each regimen received during MBC treatment
- b. Tumor response will be classified under a primary response classification as complete response (CR), partial response (PR), stable disease (SD), progressive

disease (PD), and not evaluable (NE), and unknown which comprises any other status

- c. Tumor response will be classified under a secondary response classification as matching the primary classification, but for patients with NE, responses classifiable as “Other Favorable” or “Other Unfavorable”

5) Describe PFS from the initiation of initial endocrine-based therapy

- a. Proportion of patients who are persistent to initial endocrine-based therapy for MBC at 3, 6, 12, 18, and 24 months, with persistence defined as the duration of initial regimen until one of the following events occurs: a regimen change or switch, treatment discontinuation, disease progression, or death.
- b. Landmark PFS at 3, 6, 12, 18, and 24 months
- c. Proportion alive at 3, 6, 12, 18 and 24 months

CCI

3 INTERIM ANALYSES

An interim analysis will be conducted when the data from the full complement (200 patients) treated with 1L palbociclib+LET have been collected and verified. The interim analysis will include all descriptive analyses of the palbociclib+LET cohort CCI

This will include reporting of demographic and clinical variables described in Section 4 and Section 5. CCI

CC
I

CCI

4 ANALYSIS SETS/ POPULATIONS

All patients will be selected by the patient's treating provider. **CCI**

Only patients meeting the selection criteria will be included and a patient eligibility screening questionnaire is included for each patient with programmatic checks to ensure that only qualified patients are included in the analysis set. **CCI**

4.1 FULL ANALYSIS SET

The full analysis set includes all patients who after clinical and analytical quality control assessment are retained for analysis in the study. **CCI**

CC
I

5 ENDPOINTS AND COVARIATES

The purposes of this analysis is to describe the demographics, clinical characteristics, treatment and monitoring patterns, and clinical outcomes including disease response and PFS for patients treated with 1L palbociclib+LET^{CCI}

There are four periods along the patient journey which will be characterized: at initial diagnosis of breast cancer until development of locoregional recurrent or metastatic disease (non *de novo* only), at initiation of therapy for locoregional recurrent or metastatic disease, during 1L treatment, and post discontinuation of 1L.

5.1 EFFICACY/ EFFECTIVENESS ENDPOINT(S)

The table below describes data elements to be abstracted by the provider (“Abstracted Data Points”) and independent/exposure variables calculated from the abstracted data (“Calculated Variables”). Further description of the calculation of clinical outcomes including disease response and PFS is described below the table. Variables in ***bold italics*** will be evaluated as part of the analytical assessment of data quality. Variables that are in *underlined italics* will be used in the 10% data validation exercise. These variables, along with other characteristics that may be evaluated as part of the quality control assessment are summarized below the table.

Table 2. Data Points and Calculated Variables by Role/Time Period Showing Operational Definition

Variable	Role/Time Period	Operational definition
Patient demographics	Descriptive outcome, diagnosis of breast cancer, MBC, and initiation of 1L	Abstracted Data Points: site of treatment (academic vs. community), year of birth, payer, state of residence, ethnicity, weight, height Calculated Variables: body mass index

Variable	Role/Time Period	Operational definition
Clinical characteristics	Descriptive outcome, diagnosis of breast cancer, MBC, and initiation of 1L, visceral disease used as subgroup/matching variable	
Abstracted Data Elements: weight, height, ER status, PR status, HER2 status, family history of breast cancer, date of diagnosis of advanced/metastatic disease, AJCC stage, node status, menopause status, ECOG-PS, sites of metastatic disease, comorbidities via Quan¹³ adaptation of the Charlson comorbidity index (CCI) (see Appendix 10.1 for comorbid conditions), prior cardiac toxicities, hematologic events, electrolyte abnormalities
 
Calculated Variables: age at advanced/metastatic diagnosis, age at initiation of endocrine-based therapy, time to advanced/metastatic disease, de novo metastatic disease, CCI, visceral disease at initiation of endocrine-based therapy

Neo/adjuvant treatment history	Descriptive outcome, receipt and duration of neo/adjuvant treatment used as subgroup/matching variable	
Abstracted Data Elements: chemotherapy/hormonal therapy regimens received, date of discontinuation of adjuvant treatment, receipt/date of surgery
 
Calculated Variables: disease free interval (time from discontinuation of adjuvant therapy to diagnosis of advanced/metastatic disease)

1L therapy treatment characteristics	Forms analysis set cohorts, duration of treatment is descriptive outcome	
Abstracted Data Elements: drug and/or combination endocrine partner, date of initiation, date of discontinuation, total number of cycles received, dose at initiation, dose reductions, dose increases, rationale for dose increase/decrease, treatment interruptions (e.g., drug holiday), rationale for treatment discontinuation (e.g., progression, toxicity, patient choice)
 
Calculated Variables: duration of treatment with initial endocrine-based therapy

1L therapy laboratory monitoring	Descriptive outcome	
Abstracted Data Elements: frequency of CBC, cardiac monitoring using electrolyte panel, liver function panel monitoring during first 3 cycles of therapy, date of first CBC, electrolyte panel, ECG, liver function panel
 
Calculated Variables: Time to first test during 1L therapy

Variable	Role/Time Period	Operational definition
Clinical outcomes during initial endocrine-based therapy	Primary clinical outcomes, comparison outcome for palbociclib+LET [REDACTED] CCI	Abstracted Data Elements: provider assessed response to therapy (CR, PR, SD, PD), date of best initial response (CR, PR, SD), date of disease progression, Calculated Variables: duration of stable disease
Advanced/metastatic treatment patterns following discontinuation of initial endocrine-based therapy	Descriptive Outcome	Abstracted Data Elements: drug regimens received post discontinuation of initial endocrine-based therapy (chemotherapy, switch to alternative endocrine), date of initiation and discontinuation of treatment regimens received Calculated Variables: total lines of therapy received in the metastatic setting
Status at last follow-up	Descriptive outcome, death used as part of PFS calculation	Abstracted Data Elements: date of last follow-up, receipt of hospice care, receipt of palliative care, date of death (if deceased), cause of death Calculated Variables: See section 5.1.5

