7.1. Objectives

Among MBC patients receiving palbociclib+LET according to its labeled indication as initial endocrine therapy for MBC the research objectives are to:

1. Describe the demographic and clinical characteristics of patients at the initiation of treatment:
 - a. Demographic characteristics will include age, race/ethnicity, body mass index, insurance status, state of residence at the date of MBC diagnosis and palbociclib initiation. Employment status will be assessed to the extent documented in the record. Overall duration of follow-up (months) from the initiation of palbociclib+LET will be presented.
 - b. Clinical characteristics will include year of breast cancer and MBC diagnosis, stage of initial diagnosis, menopausal status, number and sites of distant metastasis at MBC diagnosis and palbociclib initiation, verification of HER2 and ER/progesterone receptor (PR) status, histology, menopausal status at palbociclib+LET initiation, performance status and comorbid disease burden, including cardiovascular-related comorbidities (at MBC diagnosis and at palbociclib initiation), and modalities of treatment received in the neoadjuvant or adjuvant setting (chemotherapy, hormone therapy, surgery, radiation therapy).
2. Describe the frequency of laboratory monitoring for hematologic and cardiovascular toxicities during treatment:
 - a. Note that CBC monitoring and cardiac function monitoring will be assessed, but lab results/values will not be assessed under this objective.

- b. Evaluate the extent of laboratory monitoring using CBC per cycle:
 - i. The frequency of assessment of CBC with or without differential will be evaluated during the initial endocrine-based therapy for MBC.
 - c. Assess the frequency of cardiac toxicity monitoring using electrocardiogram, liver function panels, and electrolytes:
 - i. The frequency of assessment of cardiac monitoring by each method will be evaluated during the initial endocrine-based therapy for MBC.
3. Describe treatment patterns in terms of palbociclib+LET dosing, cycles received, and post-discontinuation treatment regimens:
 - a. Palbociclib dosing will include description of the starting dose, dose adjustment, discontinuation, and time to dose adjustment for palbociclib.
 - b. Duration of palbociclib in terms of the number of cycles completed prior to the discontinuation of initial treatment for MBC.

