ⁱ Participation in any interventional clinical trials following the diagnosis of metastatic or locoregionally advanced breast cancer will be flagged for further evaluation.

Variable	Operational definition
Neo/adjuvant treatment history	
Abstracted Data Elements: chemotherapy/hormonal therapy regimens received, date of discontinuation of adjuvant treatment, type of surgery, receipt of radiotherapy.
 
Calculated Variables: disease free interval (time from discontinuation of adjuvant therapy to diagnosis of advanced/metastatic disease).

Initial endocrine-based therapy treatment characteristics	
Abstracted Data Elements: Drug and/or combination endocrine partner, date of initiation, date of discontinuation, total number of cycles received, dose at initiation, dose reductions, dose increases, rationale for dose increase/decrease, treatment interruptions (eg, drug holiday), rationale for treatment discontinuation (eg, progression, toxicity, patient choice).
 
Calculated Variables: duration of treatment (DOT) with initial endocrine-based therapy.

Initial endocrine-based therapy laboratory monitoring	
Abstracted Data Elements: Frequency of CBC monitoring, dates of CBC monitoring during first 6 cycles of therapy, dates of cardiac monitoring using electrolyte panel, liver function panel, electrocardiogram.
 
Calculated Variables: None.

Clinical outcomes during initial endocrine-based therapy	
Abstracted Data Elements: provider assessed response to therapy (CR, PR, SD, PD), date of best initial response (CR, PR, SD), date of disease progression, stable disease lasting >24 weeks, favorable/unfavorable response (if stable), development of new measurable target lesions since initiation of endocrine-based therapy.
 
Calculated Variables: visceral disease at initiation of endocrine-based therapy, duration of stable disease, ORR (CR+PR+SD lasting greater than 24 weeks).

Advanced/metastatic treatment patterns following discontinuation of initial endocrine-based therapy	
Abstracted Data Elements: drug regimens received post discontinuation of initial endocrine-based therapy (chemotherapy, switch to alternative endocrine), date of initiation and discontinuation of treatment regimens received.
 
Calculated Variables: total lines of therapy received in the metastatic setting.

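### SAP Table 2 collects monitoring frequency for three cycles only and no ECG frequency, so Objective 2 can be answered only in part

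*SAP*

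**What the plan says.** **Protocol.** Objective 2 in Section 7.1 is to "Describe the frequency of laboratory monitoring for hematologic and cardiovascular toxicities during treatment". Item 2b reads "Evaluate the extent of laboratory monitoring using CBC per cycle", and 2b.i sets the period: "The frequency of assessment of CBC with or without differential will be evaluated during the initial endocrine-based therapy for MBC". Item 2c reads "Assess the frequency of cardiac toxicity monitoring using electrocardiogram, liver function panels, and electrolytes", and 2c.i adds: "The frequency of assessment of cardiac monitoring by each method will be evaluated during the initial endocrine-based therapy for MBC". The variable table in Section 8.3 lists three kinds of element: CBC frequency, with no window; "dates of CBC monitoring during first 6 cycles of therapy"; and dates of electrolyte panel, liver panel and ECG tests, with no cycle limit.

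**SAP.** Section 2.4 limits Objective 2b (CBC) to the first three cycles of first-line treatment. It does the same in 2c, which covers monitoring "using electrocardiogram, liver function panels, and electrolytes during the first three cycles of 1L treatment". Directly below, 2c.i repeats the protocol's sentence about each method during the initial therapy. In Section 5.1, Table 2 lists frequency for CBC, electrolyte panel and "liver function panel monitoring during first 3 cycles of therapy". It then lists the date of the first CBC, electrolyte panel, ECG and liver panel. The only calculated variable is time to first test.

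**The concern.** The SAP's data elements are narrower than the SAP's own objective, and narrower again than the protocol's. ECG is one of three named cardiac methods, and 2c asks how often it was done, but Table 2 records only when it was first done. Item 2c and its sub-item 2c.i also give different windows for the same quantity.

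What is at stake is one of the protocol's four objectives, which the SAP lists under its primary objectives. The charts are abstracted once, over about four weeks (Protocol 8.2), so an element left off the form could be recovered only by going back to providers. A three-cycle figure shown under an objective worded as monitoring during treatment would also be mislabelled.

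**Working it through.** The plan gives no figure to reproduce: the study is descriptive and states that no sample size calculation applies. The check sets the texts side by side.

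| Element | Protocol 7.1 (asked) | Protocol 8.3 (abstracted) | SAP 2.4 (asked) | SAP Table 2 (abstracted) |
|---|---|---|---|---|
| CBC | Per cycle, during initial therapy | Frequency, no window; dates for 6 cycles | First 3 cycles | Frequency, first 3 cycles; first date |
| Electrolytes | Frequency, during initial therapy | Dates, no cycle limit | 2c: first 3 cycles; 2c.i: during initial therapy | Frequency, first 3 cycles; first date |
| Liver panel | As electrolytes | As electrolytes | As electrolytes | Frequency, first 3 cycles; first date |
| ECG | As electrolytes | As electrolytes | As electrolytes | First date only |

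The three-cycle phrase in Table 2 could grammatically attach to the liver panel alone. SAP 2b and 2c state three cycles for all the tests, so the table applies it to all three frequencies.

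**What Table 2 can deliver**
- CBC, electrolyte and liver panel frequency in cycles 1–3. This meets SAP 2b and most of 2c.
- Whether any ECG was done, and time to the first. If the field is complete, a blank date means a count of zero.

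**What it cannot deliver**
- The number of ECGs in a patient who had at least one.
- Any frequency after cycle 3, which 2c.i and the protocol objective include.
- Dated CBCs by cycle. A count might be recorded separately for each cycle, but Table 2 does not say so.

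**Analysis section.** The visible text of SAP 7.1 mentions CBC and cardiac tests only for the 30 days before first-line treatment. Its list of what is described during first-line treatment covers dose changes, interruptions and cycles, not monitoring. No denominator is given for patients who stop early. This matters because one month of follow-up is enough for entry: 30.44 ÷ 21 = 1.45 cycles at most on the range assumed below, so an eligible patient need not reach cycle 3.

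**Scale, for illustration.** The documents give no cycle length, so 21 to 35 days is assumed. The reference is the 24.8-month median PFS of the phase III trial cited in both documents.

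Window in months = cycles × days per cycle ÷ 30.44. Share = window ÷ 24.8.

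| Cycle length | 3 cycles | Share | 6 cycles | Share |
|---|---|---|---|---|
| 21 days | 63 ÷ 30.44 = 2.07 months | 8.3% | 126 ÷ 30.44 = 4.14 months | 16.7% |
| 28 days | 84 ÷ 30.44 = 2.76 months | 11.1% | 168 ÷ 30.44 = 5.52 months | 22.3% |
| 35 days | 105 ÷ 30.44 = 3.45 months | 13.9% | 210 ÷ 30.44 = 6.90 months | 27.8% |

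**The case against.** The best defence is that the SAP made a legitimate scope choice. Protocol 8.7 allows the SAP to modify the protocol's plans and requires an amendment only for major changes to primary endpoint definitions or their analyses. Items 2b and 2c state the three-cycle window openly, so results labelled that way would mislead nobody. No PFS or response estimate is affected. The missing ECG frequency looks like a slip in a list, since 2c names ECG. The eCRF decides what is collected, and it may already be right.

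Much of this stands. The shorter window is not a breach in itself, though no reason for it is visible. The permission to modify the protocol does not, however, settle the two conflicts inside the SAP: 2c against 2c.i, and 2c against Table 2. If the ECG omission is a slip, it still needs correcting.

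A reader might also infer more than the documents support:
- **That Objective 2 cannot be answered at all.** It can in part, as the working shows.
- **That the protocol plans six cycles for every test, so the SAP halves the window throughout.** The six-cycle limit in Protocol 8.3 applies to CBC dates only. CBC frequency and the cardiac test dates carry no limit there.
- **That Table 2 yields no ECG information.** It gives any ECG and time to first ECG; the count of repeat tests is what is missing.

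**Conclusion.** The point holds as a partial loss. If the eCRF follows SAP Table 2, Objective 2 is met for CBC, electrolyte and liver panel frequency in cycles 1–3 and for any or first ECG. It is not met for repeat-ECG frequency, for monitoring after cycle 3 or for dated per-cycle CBC. Whatever the eCRF contains, the written plans disagree with each other and the SAP disagrees with itself.

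Three cycles amount to about 8–14% of the reference median PFS and six to about 17–28%. These shares rest on an assumed cycle length and on a trial's median PFS, not on treatment duration in this cohort. They show only that neither window stands for the whole of treatment. The change should be made, but the issue is confined to a descriptive objective.

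**What to change.** 1. In SAP Table 2, add an ECG count, or ECG dates, over the same window as the other tests.
2. Choose one window and state it identically in Protocol 7.1 and 8.3 and in SAP 2.4 and Table 2. There are two options:
   - Restore the Protocol 8.3 elements: CBC dates for six cycles, and dates of electrolyte, liver panel and ECG tests. State the period that the separate CBC frequency item covers, because six cycles of dates do not span treatment either.
   - Keep three cycles. Then restate Objective 2 and 2c.i in both documents as the first three cycles, and label every result that way.
3. In SAP 7.1, add an on-treatment summary of tests per cycle by method, with patients still on treatment in that cycle as the denominator.
4. Check the eCRF against the agreed list before abstraction.

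The cost is wording in both documents and, under the first option, slightly longer abstraction, most of which the protocol already planned. If the form has to change after the pre-test, Protocol 8.6 calls for resubmission to the IRB, which is a reason to settle this early.
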